## **18) Potential Benefits to Subjects**

Participants may or may not have benefit from the study. Knowledge gained through this study may aid the development of more effective treatments for individuals with alcohol dependence and other addictive disorders. There are also potential direct benefits to participants in this study. All individuals (whether assigned to the active treatment with gemfibrozil or placebo group) are receiving treatment (i.e., four sessions of motivational interviewing), and will also be offered a referral list upon completion of the study. If the medication being tested works, then individuals assigned to the intervention group may also benefit from the treatment. Also, being in a research study may provide benefit, as may taking a placebo pill; individuals who undergo a series of assessments in a research study oftentimes reduce their drinking even if they are not on active treatment. Other aspects of study participation that may be beneficial include receiving free medical and psychiatric evaluations, and the attention and support of participating in a clinical trial.

## **19) Vulnerable Populations**

No vulnerable populations will be recruited for this study.

## **20) Community-Based Participatory Research/Field Research**

N/A

## **21) Sharing of Results with Subjects/Incidental Findings**

All research MRI scans are read for incidental findings by a radiologist unless the individual has been scanned at MRN in the previous six months. If the scan is read, an e-mail notification is sent to the participant letting them know new results are available. The participant can securely log in to the COINS Homepage to access their MRI radiology report. No sensitive or identifying

information is sent via e-mail. If an abnormality that requires follow-up is identified, such as a Doctor Referral recommendation, a hard copy of the report may be mailed to the participant in addition to the e-mail notification. In these cases, the MRN Medical Director may also attempt to contact the participant by phone to explain the information and help answer questions.

## **22) Research Setting**

All study procedures and participant interactions will take place at the Mind Research Network. Study medication will be stored in a locked cabinet in a locked room once dispensed from the pharmacy. Blood samples will be processed at Tricore.

## **23) Resources Available**

The PI and study team are all experienced neuroimaging researchers. [name] serves as MRN Medical Director. Located on UNM's north campus, MRN is a 501(c)3 non-profit organization consisting of an interdisciplinary association of scientists focused on state-of-the-art imaging technology and its emergence as an integral element of neuroscience investigation.

Five private, closed door rooms are available to research staff for study visits at MRN. These assessment rooms have white noise generators outside of the doors to prevent conversations from being overheard. These are reserved by investigators as needed, and are easily accessible. The imaging facilities also have private changing rooms with lockers for personal items. In addition, there is a space for conducting blood draws that provides privacy to participants while they complete the blood draw. All MRN research staff are trained in regards to the HIPAA Privacy Rule. All individuals will be trained to administer the same consenting and study procedures. Further, all study personnel will have current CITI and HIPAA training throughout the period of the study.

## **24) Prior Approvals/Attachments Requiring Signatures**

MRN Departmental Review

## **25) Recruitment Methods**

### *1.1 Describe when, where, and how potential subjects will be recruited.*

Participants may be recruited through flyers, radio/TV ads, press releases, newspaper ads, business cards, and online postings (e.g. Craigslist, Google Adwords, Facebook, Instagram, clinicaltrials.gov) within the Albuquerque metro area. Approved study recruitment text and flyers will be used in digital recruitment mediums, such as university list-servs, online advertising mediums, or digital presentation slides. The study may also recruit using approved text/images on stickers that can be placed on paper bags and distributed at liquor stores, and study logos/information placed on bottle openers, drink koozies, and other drinking-related paraphernalia which can be handed out during local festivals (e.g. brewfests, wine festivals, state fairs, etc). Word of mouth from current and past participants, employees and collaborators, as well as other individuals will also be used and may include sharing approved information and/or recruitment materials. Finally, participants from other studies who have expressed an interest in being contacted for future studies, including from the MRN Participant Recruitment Registry, may be contacted to determine eligibility and interest in this study.

### *1.2 Describe the source of subjects.*

Participants will be volunteers from the community.

### *1.3 Describe the methods that will be used to identify potential subjects.*

Potential subjects will be self-selected and must contact the laboratory to express initial interest in the study. Once initial contact is made, research staff will explain the study and conduct a brief phone screen interview. Also, participants from other studies who have expressed an interest in being contacted for future studies, including from the MRN Participant Recruitment Registry, may be contacted to determine eligibility and interest in this study.

*1.4 Describe materials that will be used to recruit subjects. (Attach copies of these documents with the application. For advertisements, attach the final copy of printed advertisements. When advertisements are taped for broadcast, attach the final audio/video tape. You may submit the wording of the advertisement prior to taping to preclude re-taping because of inappropriate wording, provided the IRB reviews the final audio/video tape.)*

Recruitment materials are included with the application (attachments are listed below).

Brief\_advertisement\_v031118.docx

Flyer\_v1.docx

Flyer\_v2.docx

## **26) Local Number of Subjects**

We anticipate phone screening up to 100 individuals and may enroll up to 50 participants in order to obtain a final sample size of 20 participants who complete the study.

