## 4) Objectives

In this pilot study, we propose to randomize 20 participants with Alcohol Use Disorder (AUD) to treatment with either placebo or 600 mg of gemfibrozil twice daily for 4 weeks in a **double-blind placebo-controlled, clinical trial**. Participants will receive 4 sessions of motivational enhancement therapy (MET), regardless of medication assignment. Brain responses during response inhibition, stress, and alcohol cue reactivity will be measured with fMRI obtained at baseline and 2 weeks. Triglyceride levels will be obtained at baseline, 2 and 4 weeks. The protocol will be registered on clinicaltrials.gov.

**Aim 1: To investigate the effects of gemfibrozil on alcohol use at 4 weeks in individuals with AUD.** We hypothesize that relative to placebo, gemfibrozil will improve alcohol use outcomes as defined by rate of change in drinks per drinking day (DPDD), drinks per week (DPW) and percent days abstinent (PDA). Effect sizes for all 3 metrics will be calculated to determine if a larger clinical trial is warranted.

**Aim 2: To investigate the effects of gemfibrozil on various possible biological targets which are increasingly recognized as important mechanisms by which treatments for AUD work.** In particular we hypothesize that gemfibrozil will result in 1) increased engagement of cognitive control networks (inferior frontal gyrus (IFG) and dorsal anterior cingulate cortex (ACC)) during response inhibition, 2) decreased response in networks involved in reward (ventral and dorsal striatum, ACC) during the presentation of alcohol cues, 3) decreased response in networks that process negative affect [amygdala, insula, and ventromedial prefrontal cortex (PFC)] in response to emotional pictures, and 4) reduced triglyceride levels. We also hypothesize that changes in these targets will mediate the effects of gemfibrozil on alcohol use at 4 weeks.

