## 8) Study Timelines

Individual participant's involvement will last ~15 hours over 6 weeks, which includes 4 weeks of medication/placebo. We anticipate ongoing enrollment of participants for approximately 12 months.

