## 9) Study Endpoints

The study will close enrollment once 20 participants have been randomized. Based on previous medication trials for AUDs, we expect ~70-80% of participants will complete at least two weeks of the medication, which will be sufficient for deriving initial effect size estimates.

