#### Intervention

Participants who meet study criteria will be randomized to active treatment or placebo. The placebo group will receive capsules (filled with microcrystalline cellulose powder) which look identical to capsules filled with active treatment, and will receive the same number of capsules as for active treatment. Members of the study team will be blinded to study randomization; the study pharmacist and/or another honest broker at MRN (e.g. member of the Research Operations team) will be un-blinded, and the pharmacist will not interact with any of the participants. Gemfibrozil will be prescribed at 600 mg by mouth twice daily, *which is the standard FDA approved dose used for the treatment of hypertriglyceridemia*. Adherence will be monitored with bi-weekly pill counts. At the first med dispensing visit (30 minutes, baseline), participants will receive basic information about possible side effects and will be provided with a 2-week supply. During the follow-up med dispensing visit at Visit 5 (15 minutes), individuals will undergo a review of side effects.

All individuals will also receive 4 sessions of motivational enhancement therapy (MET), thus reducing ethical concerns of non-treatment. Therapists will be trained by a MINT-trained trainer.

#### Visit 4

One week after starting medication, participants will complete the second MET session. In addition, participants will complete TLFB, PACS, Helping Alliance Questionnaire, and the CIWA. Expected time: 30 minutes

### Visit 5

Two weeks after starting medication, an additional two weeks of medication will be dispensed, the third MET session will take place, and a follow-up MRI scan (identical to baseline scanning session), blood draw, and assessments will take place. The blood draw will be used to measure LFT's, GGT, and triglyceride levels. Assessments will include the CIWA to measure withdrawal, the ICS to measure impaired control, the PACS to measure craving, the TLFB to measure drinking, the Helping Alliance Questionnaire, and medication side effects. Expected time: MET (30 minutes), MRI (1 hour), Med dispense (30 minutes), Assessments/blood draw (1.5 hours)

### Visit 6

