## 16) Withdrawal of Subjects

Participants may withdraw from the study at any time. All unused study medication can be returned to study staff who will return it to the pharmacist for proper disposal.

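### Section 26 counts on 20 participants completing the study, but Section 9 stops enrolment at 20 randomised, so the target is met only if nobody is lost

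*Combined protocol and SAP*

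**What the plan says.** Section 26 (Local Number of Subjects) sets ceilings of 100 phone screens and 50 enrolled, and gives the purpose as "in order to obtain a final sample size of 20 participants who complete the study".

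Section 9 (Study Endpoints) contains the only rule for ending enrolment: "The study will close enrollment once 20 participants have been randomized". Section 4 (Objectives) likewise plans to randomise 20.

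On retention, Section 9 states "we expect ~70-80% of participants will complete at least two weeks of the medication", and adds of this level "which will be sufficient for deriving initial effect size estimates".

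Section 16 (Withdrawal of Subjects) states "Participants may withdraw from the study at any time" and says nothing about replacing those who leave. Section 8 (Study Timelines) describes a participant's course as "involvement will last ~15 hours over 6 weeks, which includes 4 weeks of medication/placebo". At Visit 5, two weeks after starting medication, Section 10 specifies that "a follow-up MRI scan (identical to baseline scanning session), blood draw, and assessments will take place".

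**The concern.** A fixed number randomised and the same number of completers are compatible only with zero loss after randomisation. The allowance of 50 enrolled can absorb people who consent and then fail the screening or medical visits. It cannot make up for anyone lost later, because enrolment closes at the twentieth randomisation.

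Two things follow. First, a single dropout makes the Section 26 figure unattainable, and the plan itself anticipates several participants stopping medication early. An outcome the plan expects would then read as a missed target. Second, the follow-up fMRI for Aim 2 is at week 2. A reader who takes 20 from Section 26 would overestimate how many follow-up scans will come from people who have had a full two weeks of medication or placebo.

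**Working it through.** **Inputs**

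- Number randomised: 20 (Sections 4 and 9).
- Target completers: 20 (Section 26).
- Proportion expected to reach two weeks on medication: 0.70 to 0.80 (Section 9).
- Ceiling on enrolment: 50 (Section 26).
- Proportion completing the study: not given.
- Replacement after randomisation: none provided.

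**1. Can the stated figure be reproduced?** There is no power calculation to rebuild; the Statistical Analysis paragraph in Section 13 says power will probably be insufficient. The only check available is number randomised × proportion retained:

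- 20 × 0.70 = 14
- 20 × 0.80 = 16

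Neither gives 20. Obtaining 20 from 20 requires retention of 20/20 = 100%. The shortfall is 20 − 16 = 4 to 20 − 14 = 6.

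**2. How likely is no loss at all?** If the 70-80% is taken as the completion rate and participants are independent, the chance that all 20 are retained is:

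- 0.70^20 = 0.0008 (0.08%)
- 0.80^20 = 0.0115 (1.15%)

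**3. How many would have to be randomised to expect 20?** Number needed = 20 / proportion retained:

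- 20 / 0.80 = 25
- 20 / 0.70 = 28.6, rounded up to 29

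That is 25 − 20 = 5 to 29 − 20 = 9 more than Section 9 allows, although both totals lie under the ceiling of 50.

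**4. What the rate does and does not cover.** The 70-80% concerns two weeks of medication, half of the four-week course. Section 26 does not define completion. It could mean Visit 5 (week 2), Visit 6 (week 4) or the phone call at week 6.

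| If completing the study means | What 14-16 represents |
|---|---|
| Exactly two weeks of medication | The expected number of completers |
| All four weeks of medication | An upper bound, since nobody completes four weeks without completing two |
| Attending a visit or call, whether or not still on medication | Neither; the plan gives no rate |

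The same limit applies to the scans. Nothing makes the week-2 scan conditional on still taking medication, so the total scanned could exceed 14-16. The number scanned after a full two weeks of medication or placebo is expected to be about 14-16 at most.

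**The case against.** The strongest reply is that nothing has been miscalculated. Section 26 uses the language of anticipation and gives ceilings and an aim; Section 9 gives a stop rule and an expected rate; no formula joins them. Section 26 may simply use completion loosely for the final randomised sample, with 50 enrolled covering screening losses. Two screening visits before baseline fit that reading. The 70-80% is also not a study-completion rate, so 4-6 short is a measured gap under one definition only. Finally, Section 9 already discloses the expected retention and calls it adequate, so the harm is one of presentation.

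Much of this stands. The size of the gap is conditional, the consequence is small, and loose drafting is a plausible explanation. None of it removes the conflict, which does not need the rate: any loss after randomisation defeats the figure in Section 26. If the loose reading is right, the same rewording cures it.

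It can also be said that amending Section 26 rather than Section 9 presumes what the sponsor meant, since 25-29 randomised would fit under the ceiling of 50. But Sections 4 and 9 agree on 20 randomised, and Section 9 holds the only closing rule. If 20 completers really was the intention, Sections 4 and 9 are the ones that need changing; the document is inconsistent either way.

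**Conclusion.** The concern holds. As written, Section 26 states a number of completers that the plan's own stop rule can deliver only with no loss after randomisation, while the plan expects losses from medication and makes no provision for replacement.

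At the plan's own rate the gap is 4-6 participants out of 20. That size rests on two assumptions: that the 70-80% applies to those randomised, and that completing the study requires at least two weeks of medication. Under any other definition the conflict remains but its size cannot be computed from the document.

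This should be fixed, but it does not threaten the design. The trial is a pilot that expects to be underpowered, and Section 9 regards the expected retention as enough for initial effect sizes.

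**What to change.** Leave the Section 9 stop rule as it is and restate Section 26 to match it. Suggested wording: *Up to 100 people will be screened by phone and up to 50 consented, so that 20 can be randomised; about 14-16 of these are expected to complete two weeks or more of study medication.* Using consented in place of enrolled is an interpretation for the sponsor to confirm.

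Two clarifications could be made in the same edit. One is to define study completion once, by naming the last required contact (for example Visit 6 or the week-6 call). The other is to say what the N=40 in Section 6 counts; it may be a figure before randomisation, but the text does not say. The verdict does not depend on either.

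The cost is a few words in Sections 6 and 26. No participants, visits, assessments or analyses are added. The one drawback is that the stated number becomes less favourable: about 14-16 two-week medication completers in place of 20 study completers. The alternative, raising the number randomised to 25-29, would add 5-9 participants and is not needed for the plan's stated purpose.

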## **27) Confidentiality**

All participants are assigned a study ID (URSI) that links their data with their name and other identifying information. All study data (with the exception of the consent form and payment receipt) are coded only with this number. The information is maintained in a secure, restricted access database. After completion of data analysis, the linking code will be made inaccessible to the research team. De-identified data will be retained until data analysis activities are complete.

## **28) Provisions to Protect the Privacy of Subjects**

Five private, closed door rooms are available to research staff for study visits at MRN. These assessment rooms have white noise generators outside of the doors to prevent conversations from being overheard. These are reserved by investigators as needed, and are easily accessible. The imaging facilities also have private changing rooms with lockers for personal items.

## **29) Compensation for Research-Related Injury**

No commitment is made by the MRN to provide free medical care or money for injuries to participants in this study. This is clearly stated in the consent form.

## **30) Economic Burden to Subjects**

Participants will not be charged for any of the experimental study procedures, including MRI scans. If incidental findings from the study result in the need for further evaluation/treatment, the participant or their insurance company will be responsible for additional clinical evaluation/treatment that may be needed. Also, incidental finding information is disclosed only to the individual participant. However, if a participant chooses to disclose such information also to their personal physician, this may become part of their medical record which may or may not have an effect in the future on getting health or life insurance.

## 31) Consent Process

Upon initial contact, the study will be briefly introduced to the participant by a member of the research team. Participants will then be screened over the phone or in person. Identifiable information will be retained for those participants who do not meet inclusion criteria only for the duration of the study to ensure that the same participant does not attempt to enroll a second time. If the participant meets inclusion criteria, the study visit will be scheduled and an informational brochure and copy of the consent document will be sent to them if requested. Participants requesting the consent ahead of their visit will be allowed as much time as they need to decide whether or not to participate, and the PI or study staff will be available to answer questions about the consent/study procedures while the participant is making their decision. When the participant arrives for their appointment, the participant will be seated in a private room and given time to read the consent form. After the participant has finished reading the consent form, the study is described more fully by the research team and the participant is asked whether they have any questions regarding the described procedures and risks/benefits. Participants must elect to participate and can choose to discontinue their participation in the study at any time. If requested, we will show the participants the equipment that will be used to perform the study. In addition, we may ask some basic questions of the participants about the proposed study to ensure that the participants understand the nature of the experiment. No coercion or undue influence will be used.

If there are no further questions, the consent form is signed and stored in a locked cabinet in a locked office at MRN. A copy of the consent will be given to the participant.

## 32) Drugs or Devices

All medications will be stored and handled by the research pharmacy and only staff trained to dispense medications including the research coordinator or study physicians will dispense medications. Medications will be dispensed at Visits 3 and 5, and pill counts/medication adherence will be measured at Visits 4-6. In addition, participants will be asked to report on adherence on the follow-up phone call.

